Our team has developed an enhanced pain coping skills protocol (i.e., Engage) to better meet the needs of older adult populations. Engage is brief, and counselors teach participants behavioral pain coping skills (such as strategic use of activity pacing for increasing physical activity) along with additional psychological coping skills such as linking behavior change to deeply held personal values. Previous work testing the Engage protocol demonstrated improvements in pain-related disability for patients with advanced cancer, many of whom were older adults. We propose to extend previous work by increasing our focus on physical activity within the Engage protocol for adults ≥ 65 with persistent OA-related pain. Specifically, we will integrate the behavioral physical activity component of Engage with physical activity monitoring using wearable technology and tailor it for older adults with OA. This critical step will provide important data to support the testing of a brief, adapted protocol for this population.

Engage-PA will leverage technology, strategic activity pacing and goal setting, and linking physical activity goals (i.e., average daily steps walked) to meaningful personal values clarification (e.g., enhancing the quality of time spent with grandchildren) to increase physical resilience via physical activity in older adults. The integration of these particular physical activity components for this population is novel. While existing protocols for enhancing physical activity in this population may utilize activity pacing types of interventions along with other psychological coping strategies, none to date have incorporated such a strategic focus on deepening personally meaningful values as a means of increasing motivation with those methods. Further, we are integrating these behavioral strategies while also providing participants with ongoing direct feedback on their physical activity from their personal fitness tracker that can be discussed with a provider as an additional source of positive accountability for physical activity goal setting. Such technology extends the intervention by bringing it into participants' daily life, maximizing the potential for positive behavior change from even brief counseling support.

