Measures. Age, race/ethnicity, marital status, medical comorbidities, exercise patterns, medical care utilization, height and weight, use of pain medications, and COVID-19 impact will be collected via self-report and electronic medical record review. **Screening:** Recruitment Screening phone script uses items from the Physical Activity Readiness Questionnaire Plus (January, 2020 version) tailored for this study to assist in assessing for eligibility and safe participation, and assist staff in determining if participants need to discuss exercise with their medical team prior to enrolling in the study. Folstein Mini-Mental Status Exam will be utilized to determine if participants have more than mild cognitive impairment that could prevent safe participation in the study. A cut off score of 19 will be used, which is the lower bound of mild cognitive impairment. **Clinical Tool:** Rating of Perceived Exertion scale. This is a 0-10 scale with anchors for personally-determined exertion levels as participants engage in activity. **Primary Outcomes.** Feasibility will be measured by recruitment rate, at least 75% accrual (N=50), retention ($\leq 20\%$ attrition), and adherence as measured by use of fitness-tracker for $\geq 75\%$ of days participating in the study. Acceptability will be measured by $\geq 80\%$ of participants reporting being “very satisfied” with the program using a standardized measure, the Client Satisfaction Questionnaire. Secondary outcomes will be collected at baseline, post-treatment, and 1 month follow up. Physical resilience will be measured via Garmin fitness tracker daily steps tracked for 7 consecutive days at each timepoint and continuously throughout the study. Pain-related disability will be assessed with the self-reported Arthritis Impact Measurement Scale (AIMS) which assesses functioning across several areas such as physical mobility, social activity, and activities of daily living. Psychological well-being will be measured by 1) the AIMS Mood and Tension subscales, which measure depression and anxiety, 2) Bulls-Eye Values Survey where participants are asked to rate how successful they have been in living consistent with personal values across life domains of health, relationships, work/community, and leisure, and 3) The Acceptance and Action Questionnaire-II, which is a 7-item questionnaire assessing psychological flexibility, which is a common measure used to assess psychological well-being. The Coronavirus Impact Scale will rate the impact of the COVID-19 pandemic, and was developed to widely cover types of adversities individuals’ experienced secondary to the pandemic. The scale is used commonly in numerous large studies in response to clinical and

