Enrollment and assessment procedures. Interested participants will meet with study staff to conduct informed consent and complete the baseline assessment, and then be randomized to either Engage-PA or TAU+. All participants will complete self-report questionnaires at baseline and post-treatment. Self-report data using measures as listed above will be collected online using RedCAP or paper/pencil. All participants will be given a personal fitness-tracker (ie., Garmin ViVoFit) at baseline for use throughout the study, with instructions on how to write down daily steps for 7 consecutive days at baseline and post-treatment assessments, as well as continuous measures of daily steps in the intervening period. Number of daily steps as read by the Garmin will be collected via paper and pencil and sent to study staff via telephone, text, email or participants can come to the research staff offices for syncing and daily steps data will be recorded directly from the Garmin devices and devices then returned to participants. All daily steps data will be de-identified and coded using a Study ID. Data will be collected on Duke servers and managed by Duke study staff. This data will be collected and stored using a unique Study ID, and will not include PHI. Participants will be compensated for their time completing both assessments (\$30 each, for up to \$60).

Engage-PA Intervention. Engage-PA participants will attend two 45-minute sessions with a study therapist two weeks apart. Session 1. Participants will learn to apply the Activity-Rest Cycle for strategic pacing of physical activity while also avoiding extreme pain, and this practice is graded to increase stamina over time. Participants will select a physical activity (e.g., walking), and set a specific physical activity goal (e.g., walk for 10 minutes two times per day) for practice between sessions. Participants may choose to walk or exercise in their homes or communities at times and places of their choosing. Participants will be coached on the use of the Rating of Perceived Exertion Scale for rating how intense they experience walking or other exercise. Participants will be encouraged to keep their perceived exertion level at or below 5 on

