TAU Plus Personal Fitness Tracker condition. The treatment as usual group will be monitoring only. They will continue to receive standard care throughout the study, and there will be no intervention. They will be given a personal fitness monitor as a continuous monitoring device for the steps walked. They will be given basic instructions on the device's use and data from the device will be collected (only during the study period). They will not be asked to engage in any particular form of exercise, or specifically be asked to increase their walking. However, they will be given the Ratings of Perceived Exertion Scale, and informed that study members will contact their medical team before they initiate a new exercise program to gain permission of enrolling in a study that will increase or start physical activity, and participants will be encouraged to talk to their doctor if they plan to engage in activity above a 5/10 on the RPE Scale. They will also be encouraged to continue monitoring any medical conditions using at-home monitoring devices as recommended by their treating medical team (e.g., blood pressure cuff, glucose monitors) if they had previously been using those monitoring devices. They will not receive the 2 session intervention protocol, and no specific goals for steps or other activity will be set by the study staff.

Selection of Subjects

We plan to enroll a maximum of 50 adults age 65 or older with a diagnosis of OA in the knee or hip who are currently served by Duke clinics. Letters will be mailed to potentially eligible patients identified through electronic health records (i.e., DEDUCE) and follow up phone calls will assess participant interest and conduct eligibility screening. Our study team has successfully recruited using these methods in large, NIH funded behavioral pain management trials.

Eligible participants:

- age 65 or older
- English speaking
- diagnosis of osteoarthritis in knee or hip (as verified by medical record review)
- able to ambulate even if assisted with walker or cane
- endorse worst pain AND pain interference as \geq 3 out of 10 within the last week

Exclusion criteria:

- planned surgery during study duration that would limit mobility (e.g., due to recommended rehabilitation or recovery period) for more than 3 weeks
- current enrollment in cardiac rehabilitation
- myocardial infarction in the past 3 months
- major surgery requiring limited movement or mobility for recovery within the past 3 months

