contacting potential participants' medical teams for confirmation that their patient's health is managed and gain approval to enroll in the study that would require the physical activity of walking. Primary care teams will be contacted first, and if needed, specialty care providers will be contacted. DEDUCE pulls organized by Duke Primary Care clinics will be used to identify potential participants with OA, and as such, all potential participants shall have seen a Duke PCP. If a provider requests a release of information, patients will be provided one to sign to permit the discussion of their health information solely for the purpose of determining eligibility if they so choose.

Informed consent procedures will be conducted either in person, online using REDCap or via phone. Once informed consent has been received, participants will be scheduled for a study appointment either to happen at that time or a time convenient for them in the future. A member of the study team will conduct the appointment. If a participant declines study participation at any point during these procedures, the information provided to the study team through DSR/DEDUCE/Maestro will be immediately de-identified. At this first study appointment, the study team member will explain all study procedures and administer the baseline assessment. After the patient has consented and completed the baseline assessment, they will be randomized to either receive: 1) Engage-PA or 2) Treatment As Usual plus use of personal fitness tracker.

Based on previous work with this population, we expect that approximately 50% of the sample to be male and 50% female. Based on the ethnic make-up of patients coming to Duke clinics, we anticipate that the ethnic make-up of the sample will likely include Caucasian (75%), African-American (15%), Asian (5%) and Hispanic (5%). Recruitment efforts will focus on actively seeking to attract an ethnically diverse sample representative of demographics of the local recruitment area.

Participants will be compensated \$30 for their time when they participate in baseline and post-treatment assessments, for a total of up to \$60 per participant.

Risk/Benefit Assessment

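### Is the seven-day baseline step record made before or after randomisation?

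*Combined protocol and SAP*

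**What the plan says.** Under Enrollment and assessment procedures the order is: "Interested participants will meet with study staff to conduct informed consent and complete the baseline assessment, and then be randomized". The same section deals with the device: "All participants will be given a personal fitness-tracker (ie., Garmin ViVoFit) at baseline for use throughout the study", and it comes "with instructions on how to write down daily steps for 7 consecutive days at baseline and post-treatment assessments". The Measures paragraph makes this record the step outcome: "daily steps tracked for 7 consecutive days at each timepoint and continuously throughout the study".

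Subject Recruitment and Compensation adds the setting: "At this first study appointment, the study team member will explain all study procedures and administer the baseline assessment". Once consent and that assessment are complete, "they will be randomized to either receive: 1) Engage-PA or 2) Treatment As Usual plus use of personal fitness tracker".

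The section on the TAU Plus Personal Fitness Tracker condition says of the control arm: "They will be given a personal fitness monitor as a continuous monitoring device for the steps walked".

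In Purpose of the Study, H2a is a secondary comparison of daily steps over time (baseline and post-treatment) and between groups. The same section has every participant measured with the Garmin device for the whole study.

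**The concern.** Three features suggest that the baseline week might follow allocation.

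- Consent and the baseline assessment take place at a meeting with staff. A seven-day record on a device first issued at baseline cannot be finished at that meeting.
- The tracker appears in the wording of what control participants are randomised to receive.
- The control-arm section describes handing over the monitor without referring back to its issue to everyone at baseline.

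If the week did follow allocation, participants who knew their arm would record the baseline for H2a. If it also ran past Session 1, Engage-PA participants would be recording baseline steps while already working towards an activity goal. Background & Significance describes such goals in terms of the H2a measure itself: "linking physical activity goals (i.e., average daily steps walked) to meaningful personal values clarification". Any early rise in steps would then be absorbed into the baseline and would shrink the between-arm difference in change.

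**Working it through.** **1. The sections side by side**

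| Section | Order stated | Tracker timing stated |
|---|---|---|
| Enrollment and assessment procedures | consent, completed baseline assessment, randomisation | at baseline, to all |
| Subject Recruitment and Compensation | the same order | none; tracker named in the control arm's label |
| TAU Plus Personal Fitness Tracker condition | none | none |
| Purpose of the Study | none | all participants, throughout the study |
| Engage-PA Intervention | Session 1, then Session 2 two weeks later | Session 2 reviews tracker data |

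The only two sections that give an order give the same one. No section puts tracker issue or the step week after randomisation.

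**2. Can the control-arm wording carry a time?** Suppose it meant that the device is supplied by allocation to the control arm. Engage-PA participants would then have none. That conflicts with issue to all at baseline, with the statement in Purpose of the Study, and with the use of tracker data in Session 2. The wording makes sense as a description of the comparator: usual care, with the device that everyone wears.

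**3. Day count.** The plan gives no figure on this point. Its one derived figure, 50 × (1 − 0.20) = 40 participants after attrition, reproduces but does not enter here. Let the device be issued on day 0, the record cover days 1 to 7, and randomisation follow record day r. The number of baseline days after allocation is k = 7 − r.

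- Record completed first (r = 7): k = 7 − 7 = 0.
- Randomisation at the end of the first appointment (r = 0): k = 7 − 0 = 7.
- Randomisation part-way (r = 1 to 6): k = 6 to 1.

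The range is therefore 0 to 7, and the stated order, with the record counted as part of the assessment, gives 0.

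**4. What k could do to H2a.** This is an illustration only, because the documents give no effect size or standard deviation. Let f be the assumed share of the intervention effect already present on baseline days after allocation. A difference in change scores keeps 1 − f × k/7 of the effect. With baseline adjustment at an assumed slope of 0.5 it keeps 1 − 0.5 × f × k/7.

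| f | k = 0, either method | k = 7, change score | k = 7, adjusted |
|---|---|---|---|
| 0 | 100% | 100% | 100% |
| 0.25 | 100% | 75% | 87.5% |
| 0.5 | 100% | 50% | 75% |
| 1 | 100% | 0% | 50% |

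The loss needs both k > 0 and f > 0. If Session 1 comes after the week, f may be near 0 even when k = 7, which leaves mainly the effect of knowing one's arm. No section places Session 1 inside the baseline week.

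**The case for a change.** The strongest case for a change is practical. The plan describes no waiting period, return contact or check of the step record before randomisation. It does not say outright that the seven-day record is part of the assessment that must be complete. Staff who take the single appointment at face value could randomise the same day, so that all 7 days fall after allocation. Session 1 is not dated relative to the step week, and the analysis section does not define baseline steps. A single sentence would settle the matter.

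The silence is real, and so is the 0 to 7 range. But it is silence and not a wrong rule. The procedural section ties the seven-day record to the baseline assessment, and both sections that give an order put randomisation after that assessment is completed. Staff who follow this obtain a baseline before allocation. The more serious harm needs two further conditions that no section states: randomisation before the week is finished, and a week that runs past Session 1. The worked example of a goal under Engage-PA Intervention is also in minutes of walking; the link to daily steps rests on a parenthesis in the background. The claim that the sections contradict each other does not stand.

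**Conclusion.** No change to the plan is needed. The sections do not disagree. They leave one scheduling detail unstated, and the natural reading fills it soundly, with 0 of 7 baseline step days after allocation. The outer bound is 7 of 7, reached only if randomisation is done at the first appointment before any step day is recorded. The resulting effect on H2a cannot be estimated from the documents.

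This rests on two assumptions: that the seven-day record belongs to the baseline assessment, and that staff wait for it before randomising. If practice differed, the remedy would lie in reporting. The week would be labelled as recorded after allocation, and a comparison of post-treatment steps between the randomised groups would not depend on it. The stakes are limited to one secondary outcome in a feasibility pilot of 50. No primary outcome uses baseline step counts, and no sample-size figure depends on the point. A clarifying sentence would be harmless, but it is editing and not a correction.

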a 10 point scale (10 being the max exertion), unless they had previously engaged in a vigorous activity program or have discussed initiating a new physical activity (other than walking) with their doctor. They will also be encouraged to continue monitoring any medical conditions using at-home monitoring devices as recommended by their treating medical team (e.g., blood pressure cuff, glucose monitors) if they had previously been using those monitoring devices. They will also identify and clarify deeply meaningful personal values (e.g., connection with loved ones) as motivation for increasing physical activity. Participants will link their personal values to their physical activity goals either directly (e.g., playing with grandchildren, walking the dog) or indirectly (e.g., being healthier furthers such activities as helping others, spending quality time with friends, being less dependent on others and increased financial stability, etc.). Session 2. Participants will review their personal exercise goal using their personal fitness monitor data with the study therapist, troubleshoot issues using the Activity-Rest Cycle, further clarify personal values for increasing physical activity, and set longer term physical activity goals. Participants may choose to walk or exercise in their homes or communities at times and places of their choosing. Study sessions will be audio recorded using a Duke issued tablet device.

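### Engage-PA Session 1 lifts the 5/10 exertion advice for anyone with a past vigorous program, even a lapsed one, without a doctor discussion: a minor safety wording point

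*Combined protocol and SAP*

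**What the plan says.** In the combined protocol and SAP, under Design & Procedures, the Engage-PA Intervention paragraph coaches participants in Session 1 on the Rating of Perceived Exertion scale. It then gives the intensity advice: "Participants will be encouraged to keep their perceived exertion level at or below 5 on" a 10-point scale, "unless they had previously engaged in a vigorous activity program or have discussed initiating a new physical activity (other than walking) with their doctor". The next sentence tells participants to continue home monitoring of medical conditions "if they had previously been using those monitoring devices".

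The TAU Plus Personal Fitness Tracker paragraph sets no exertion ceiling. It hands out the same scale and says that "participants will be encouraged to talk to their doctor if they plan to engage in activity above a 5/10 on the RPE Scale". It also says that study members will contact the medical team before a new exercise program starts, "to gain permission of enrolling in a study that will increase or start physical activity".

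Selection of Subjects excludes recent events by look-back. Two of these exclusions read "myocardial infarction in the past 3 months" and "major surgery requiring limited movement or mobility for recovery within the past 3 months"; the third covers falls within the last 3 months that led to immediate treatment or hospitalization. Two further exclusions bear on exercise safety: "current enrollment in cardiac rehabilitation", and a provider's view that exercise should only be supervised.

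**The concern.** The first route out of the 5/10 advice has no time limit, no requirement that the program be continuing, and no doctor contact. The population is aged 65 or older with painful knee or hip osteoarthritis, and the Background says that this condition often reduces physical activity. A vigorous program that has lapsed is therefore a foreseeable history. Having exercised hard at some earlier time says little about whether exertion above 5/10 suits the person now, least of all when the program ended before a heart attack, major surgery or a treated fall.

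At stake is participant safety in advisory text. Participants exercise at home or in the community, where the Risk/Benefit Assessment acknowledges a minimal risk of exercise-related injury or falls and judges the benefits to outweigh it.

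**Working it through.** No formula or stated figure applies, so the check compares the texts.

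**Step 1: the exception.** It has 2 routes joined by *or*. One needs a doctor discussion; the other (past vigorous program) does not and carries no currency requirement. The TAU+ doctor prompt has 0 exceptions.

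**Step 2: is *previously* limited elsewhere?** Measures, Screening procedures, Selection of Subjects, and Subject Recruitment and Compensation contain no definition or time window for prior vigorous activity.

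**Step 3: do the exclusions close the gap?** Three stop at 3 months (heart attack, major surgery, treated fall). Two more (cardiac rehabilitation, required supervision) shrink the exposed group. None of the 3 + 2 = 5 refers to exertion level after enrolment. For example, a person four months past a heart attack, whose vigorous program ended before it, can be eligible and meets the exception read literally.

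**Step 4: the arms by exercise history, as written.**

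| Participant | Engage-PA, Session 1 | TAU+ |
|---|---|---|
| No vigorous history, no doctor discussion | Advised to stay at or below 5/10 | No ceiling; doctor prompt above 5/10 |
| Currently vigorous | No ceiling, no prompt | No ceiling; doctor prompt above 5/10 |
| Lapsed vigorous program | Literal reading: no ceiling, no prompt. Established-activity reading: ceiling applies | No ceiling; doctor prompt above 5/10 |
| Has discussed a new activity with a doctor | No ceiling; discussion already held | No ceiling; doctor prompt above 5/10 |

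Engage-PA is stricter in the first row. Its text gives less than TAU+ only where the past-activity route applies (second row, and third row read literally). The third row is the one that matters for safety.

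**Step 5: other safeguards.** Readiness-questionnaire items and encouragement to discuss walking or other exercise operate before enrolment, in both arms. Medical-team contact under Screening procedures follows from unmanaged conditions and seeks approval for a study requiring walking; the broader wording stands only in the TAU+ paragraph. Activity-Rest pacing still applies to people using the exception, but it sets no exertion limit. These reduce the risk; none is stated to govern exertion above 5/10 once a person is enrolled.

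**The case against.** The strongest reply is that lapsed activity is not the natural reading. The sentence sets prior vigorous activity against starting something new, which suggests established versus new. Restarting an abandoned program is closer to starting, and that goes to the doctor. The following sentence uses the same adverb for devices already in use. This stands as a plausible account of intent. It does not settle the text: in the device sentence the sense of continuity comes from the instruction to continue monitoring, and the exertion clause has no such word.

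A second reply is that the arms are not compared like for like, since one has a ceiling and the other a prompt. That stands. A reader might infer that the arm urged to be more active is less protected overall. The documents do not support this: outside the exception its advice is stricter, and it has more coaching.

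A third reply is that everyone has already been encouraged, before enrolling, to discuss exercise with their medical team, with no exertion limit on that encouragement. This also stands, so what is missing is a repeat at the moment the exertion advice is lifted. The therapist's session materials and the phone script, where the clause could be put into practice, are not in the documents.

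**Conclusion.** The point holds as a minor, optional wording improvement for participant safety. Followed literally, Session 1 removes its only stated intensity advice for someone whose vigorous activity is in the past, with nothing in its place.

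The number exposed cannot be derived. The 25 planned Engage-PA participants are those who hear the advice, not those at risk. Exposure needs a lapsed vigorous program and a decision to exceed 5/10; the more worrying case also needs an event outside the 3-month window that screening did not pick up. Probably few people meet this.

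A reader might infer a demonstrated safety failure, or that people recovering from heart attacks are being sent to exercise hard. The documents show neither: the clause is ambiguous, the advice is encouragement rather than an enforced limit, and several safeguards come before it. The feasibility outcomes are unaffected, as are sample size and analysis. The conclusion concerns the protocol text only and assumes that the session materials do not already restrict the exception to current activity.

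**What to change.** Make two edits to Session 1:

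1. Change *had previously engaged* to *are currently engaged* in the exception, keeping the doctor-discussion route.
2. Add the existing TAU+ sentence for all Engage-PA participants, so that anyone planning activity above 5/10, whatever their exercise history, is encouraged to talk to their doctor.

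The first edit keeps the ceiling for people whose program has lapsed, unless they have used the doctor route. The second gives both arms the same prompt. The TAU+ text stays as it is. No event-history question is needed, because the prompt does not depend on history, and nobody has to judge whether self-reported resumption after a heart attack is enough.

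The cost is one phrase changed and one sentence added, with no new visits, staff or measures. The downside is that some current or past vigorous exercisers will be prompted to have a doctor conversation they may not need. If current activity was always the intent, the first edit simply states it.
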